### **5.11.3 Clinical Global Impressions - Severity**

The CGI-Severity (CGI-S) is a single-item score from a 7-point rating scale used to assess the investigator's global impression of severity of psychosis as it relates to this study population. Scores range from 1 (Normal, not at all ill) to 7 (Among the most extremely ill patients). Scores of 0 indicate 'Not Assessed' and will be converted to missing. The CGI-S will be performed at each post-baseline study visit.

The observed values of CGI-S will be summarized for each study visit. The data were also summarized within each geographic area (North America and outside North America).

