## DEFINITIONS

The following definitions are developed for the purpose of statistical analysis and data tabulation.

Adverse Event	An adverse event (AE) is any untoward medical occurrence or unintended change from the subject's pre-treatment condition, including inter-current illness, that occurs during the course of a clinical trial after treatment has started, whether considered related to study treatment or not. An AE can therefore be any unfavorable and unintended sign (including an abnormal laboratory finding, for example), symptom, or disease temporally associated with the use of a medicinal product, whether or not considered related to the medicinal product.
Baseline	Baseline is defined as the last available measurement taken prior to the first study drug administration in the ACP-103-015 study. If an ACP-103-015 baseline assessment was not scheduled to be performed, then the baseline value will be taken from the last available measurement in the core study.
Change from Baseline	For any given parameter at any given visit, the change from baseline (CFB) is defined as the parameter value for the given visit minus the Baseline value.
Descriptive Statistics	Number of subjects, mean, median, standard deviation, standard error of the mean, minimum and maximum for continuous measurements; number and percentage of subjects in each level of a categorical measurement.
Safety Analysis Set	The safety analysis set includes all enrolled subjects who receive any study drug in the ACP-103-015 study.
Safety Assessments	

• Adverse events

• Vital Signs

• Clinical Laboratory Tests

• Electrocardiogram (ECG)

• Physical Examinations

Baseline Procedures	Subjects enrolled within 1-week of completing the double-blind period a previous trial with pimavanserin are not required to undergo baseline procedures (except an update to the medical history and baseline RUD-Lite, Appendix A ). If they were enrolled after 1-week, all baseline procedures were required.

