## **5 STATISTICAL CONSIDERATIONS**

### **5.1 General Statistical Procedures**

Statistical summaries will be generated using SAS® software, version 9.3 or higher. No formal statistical tests will be conducted. Unless otherwise specified, continuous parameters will be summarized using the following descriptive statistics: number of observations, mean, median, standard deviation (SD), standard error of the mean (SEM), minimum and maximum. Categorical parameters will be summarized using the number and percentage of subjects in each level of a category.

Descriptive statistics will be presented using a significant figure rule: the minimum and maximum will have the same number of significant figures as the data; the mean and median will have one more significant figure than the data being summarized; the SD and SEM will have two more significant figures than the data being summarized; and the sample size (n) will be reported as an integer.

Unless otherwise indicated, descriptive statistics will be reported for observed cases only and missing data will not be imputed. Missing observations will not be taken into account when calculating frequencies, unless otherwise indicated. By-visit summary tables will include all available subjects' data up to 4 years (192 weeks) on study, and any data beyond that point will be summarized in a single visit (>192 weeks). For laboratory, vitals, and ECGs by time period summaries an additional last assessment will be included.

Data listings will include all data for all subjects. Listings will present data sorted by site number, subject identification, study day, and visit (both nominal and derived, if applicable), unless otherwise specified. If a listing includes a derived visit, then in those cases where a subject has more than one result in the derived visit window the result that is used for analysis will be flagged in the listing.

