### 5.4.3 Missing Values

Unless otherwise specified, missing values will not be imputed for any of the rating scales or questionnaires. A missing value is defined as one which is blank, not done, or not applicable on the eCRF. If a scale has a “Not Assessed” response, then that value will be considered a missing value for analysis. In addition, if one or more items in a given subscale is missing then the entire subscale will be set to missing. In case a questionnaire consists of more than 1 subscale, any non-missing subscales will be used for analysis. For example, if in the SAPS scale the Hallucination subscale has a missing item, but the Delusion subscale is complete, then the Delusion subscale will be analyzed per the analysis plan. For the CGI-S and CGI-I questionnaires, a response of “Not assessed” will be treated as a missing value as well.

For questionnaires that utilize a total score (NMSS, Caregiver Burden Scale), if any of the individual items that contribute to the total score are missing, the total score will also be set to missing.

Missing baseline assessments will not be imputed. However, the SAPS and CGI-S scales were not collected at the ACP-103-015 baseline; therefore, the last core study assessment will serve as the ACP-103-015 baseline assessment for these scales.

Missing dates for AEs and concomitant medications will be imputed for the purpose of establishing the time of event in relation to study treatment. All data listings will display data as reported on the eCRF. When AE onset date or concomitant medication dates are missing or incomplete, the study days (onset or start day relative to first dose date) will be calculated based on imputed value.

The imputation rules for AE/concomitant medication start dates are as follows:

- If a full date is missing, impute date as date of first dose (study day 1);

- If the day component is missing from full date, date is imputed as study day 1 if the date is in the same month and year as first dose, otherwise impute as the 1st of the month;
- If the month and day components are missing from full date, but year is present, the date is imputed as January 1 if the year is different than the year of first dose, or imputed as the first dose date if the year is the same as the year of first dose;
- If any of the above imputations result in a start date which is later than an existing complete end date, the start date will be set equal to the end date.

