## **5.5 Subject Enrollment and Disposition**

Subject enrollment by protocol amendments and subject counts by study center and prior study will be summarized.

A summary of subject disposition will display the number of subjects enrolled, received study drug, and remained in the study (using visit dates recorded on the vital signs CRF) at the beginning of the following time periods: first 4 weeks (Study Days 1 to 28), 1 to 3 months (Study Days 29 to 91), >3 to 6 months (Study Days 92 to 183), >6 month to 1 year (Study Days 184 to 365), >1 to 2 years (Study Days 366 to 730), >2 to 3 years (Study Days 731 to 1095), >3 to 4 years (Study Days 1096 to 1461) and >4 years (Study Days >=1462). Also included in this summary will be subject discontinuations showing the number of subjects who terminated from the study according to the reason for study termination/discontinuation (Investigator reported and Sponsor re-classified). Reasons for study termination will also be summarized by the time period specified above.

The withdrawal reasons as reported by the investigators on the eCRF are:

- Adverse event
- Death
- Disease progression
- Subject's voluntary withdrawal of consent (Voluntary withdrawal of consent)
- The Investigator determines that continuation in the study would be detrimental to a subject's well-being because of development of a serious illness, any other significant change in clinical status, or any other compelling medical reason (Investigator decision)
- Subject fails to comply with protocol requirements (Subject non-compliance)
- Lost to follow-up
- At discretion of Sponsor (Sponsor decision)

To better understand the discontinuation pattern, ACADIA reviewed the withdrawal reasons and in some cases, on the basis of verbatim comments in the eCRF, re-classified the reasons for discontinuation using the following categories:

- Adverse event
- Death
- Lack of efficacy / PDP progression
- PD /Concomitant disease progression
- Voluntary withdrawal of consent
- PDP improvement
- Investigator decision
- Subject non-compliance
- Lost to follow-up
- Sponsor decision

Subject disposition and study completion by Investigator-specified and Sponsor-reclassified reasons for termination will be presented in data listings and summary tables. Dispositions will also be summarized by 3 regions: North America (US and Canada), Europe and India.

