### **5.11.2 Caregiver Burden Scale**

The Caregiver Burden Scale (CBS) is a 22-item questionnaire completed by the subject’s caregiver. Each item is rated on a scale of 0 - 4 where 0 = never, 1 = rarely, 2 = sometimes, 3 = frequently, 4 = nearly always. The total score of the Caregiver Burden Scale will be derived as the sum of the 22 items, with a possible range of 0 to 88. The total score and change from baseline will be summarized by visit. The data will also be summarized within each geographic area (North America and outside North America).

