### **5.11.4 Clinical Global Impression – Improvement**

CGI-Improvement (CGI-I) is a single-item score from a 7-point rating scale assessed only at post-baseline visits and is used to assess the improvement in subjects' overall psychotic condition. The 7-point scale ranges from 1 (Very much improved) to 7 (Very much worse). Scores of 0 indicate 'Not Assessed' and will be converted to missing.

The observed values for Clinical Global Impression of Improvement (CGI-I) will be summarized by visit. Additionally the proportion of CGI-I responders [with responder defined as a subject with a score of 1 (very much improved) or 2 (much improved)] will be summarized by visit. A CGI-I rating of 1 (very much improved) or 2 (much improved) represents the point at which clinically meaningful improvement in psychotic symptoms would be expected.

The observed mean values and the CGI-I responders data will also be summarized within each geographic area (North America and outside North America).

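### CGI-S is summarized only as observed values by visit although a CGI-S baseline is defined, so the by-visit means mix within-subject change with a change in who remains

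*SAP*

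**What the plan says.** - **CGI-S summary.** SAP 5.11.3: "The observed values of CGI-S will be summarized for each study visit". The same summary is repeated within each geographic area. No change from baseline is specified.
- **CGI-S baseline.** SAP 5.4.3 notes that SAPS and CGI-S were not collected at the extension baseline, and says "the last core study assessment will serve as the ACP-103-015 baseline assessment for these scales". The SAP Definitions also define change from baseline for any parameter, but no section applies it to CGI-S. CGI-S is not among the baseline questionnaire scores in SAP 5.9.1. At most it would appear as the Baseline row allowed by the visit windows in SAP Table 1.
- **Neighbouring scale.** SAP 5.11.2, on caregiver burden: "The total score and change from baseline will be summarized by visit".
- **Missing data and length.** SAP 5.1: "descriptive statistics will be reported for observed cases only and missing data will not be imputed" and "By-visit summary tables will include all available subjects' data up to 4 years (192 weeks) on study", with later data pooled into one further visit.
- **CGI-I.** SAP 5.11.4: "The observed values for Clinical Global Impression of Improvement (CGI-I) will be summarized by visit". The responder proportion by visit is also planned.
- **Reasons for leaving.** The sponsor's re-classified list in SAP 5.5 includes "Lack of efficacy / PDP progression". It also includes improvement of the psychosis.

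**The concern.** A mean over whoever attends a visit moves for two reasons: subjects change, or the group attending changes. The planned CGI-S table cannot tell these apart, because it never sets a subject's later score against that subject's own baseline. It also does not show the baseline level of the subjects who contribute to each visit.

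This deserves attention because CGI-S is the only psychosis severity rating planned for summary beyond Month 1 that has a baseline value. SAPS is given at Month 1 only, and CGI-I is a post-baseline rating. A reader looking for the long-term course of severity will turn to this table. A drift in either direction could be taken for improvement or worsening when it partly or wholly reflects departures.

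**Working it through.** The plan states no figure to reproduce: SAP 2.4 gives no sample size calculation and SAP 5.1 plans no tests. The check is therefore a selection calculation.

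**Decomposition.** Let b be the baseline score, c the change, y = b + c the score at a visit, and R the event of being observed there. Then

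mean(y | R) − mean(b) = mean(c | R) + [mean(b | R) − mean(b)].

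The left side is what a reader takes from the observed-value table. The first term on the right is the paired change. The bracket is the shift in who is observed. The plan reports neither right-hand term.

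**Inputs, all assumed.** Baseline CGI-S is normal(3.5, 1.2), rounded and limited to 1–7, which gives probabilities 0.048, 0.155, 0.298, 0.298, 0.155, 0.042, 0.006 and mean 3.506. Retention is 70%, 50% or 30%. The log-odds of leaving rise by k = 0.25, 0.5 or 0.75 per point.

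**Case 1: no subject changes.** Retention at score s is r(s) = 1/(1 + exp(−(a − k·s))), with a solved to give the overall retention. The mean among those remaining is Σ p(s)·r(s)·s / Σ p(s)·r(s).

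Worked cell, k = 0.5 and 50% retained: a = 1.752. Retention runs from 77.8% at score 1 through 56.3% at 3 and 32.1% at 5 to 14.8% at 7. The remaining mean is 3.164, so the shift is 3.164 − 3.506 = −0.342.

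| k per point | 70% retained | 50% | 30% |
|---|---|---|---|
| 0.25 | −0.11 | −0.18 | −0.25 |
| 0.50 | −0.21 | −0.34 | −0.48 |
| 0.75 | −0.29 | −0.47 | −0.67 |

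The paired change is exactly 0 in every cell. A separate run with baseline means 3.88 and 3.36, retention of 60%, 40% and 25%, and odds ratios of leaving of 1.25, 1.5 and 2.0 per point gave shifts of −0.14 to −0.75.

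**Direction.** If milder subjects leave instead (k = −0.5), the shifts are about +0.2, +0.3 and +0.5 at 70%, 50% and 30% retained. The documents name exit reasons of both kinds and do not say which will dominate.

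**Case 2: scores change, with true mean change 0.** Individual changes have SD 1.0 (assumed), and leaving depends on the current score. At 50% retained:

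| k per point | Shift in observed mean | Paired change | Shift in matched baseline mean |
|---|---|---|---|
| 0.25 | −0.29 | −0.12 | −0.17 |
| 0.50 | −0.54 | −0.22 | −0.32 |
| 0.75 | −0.72 | −0.29 | −0.42 |

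The last two columns add to the first within rounding. The share of the artefact left in the paired change is the share of the variance of y that is due to change: 1.0² / (1.2² + 1.0²) = 1.00 / 2.44 = 0.41. Paired change thus removes about 60% of the artefact.

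**The case against.** **The plan does what the protocol asks.** The objective is long-term safety and tolerability. Protocol 12.2 promises only descriptive statistics for the rating scales at each visit, and SAP 5.11.3 delivers that. No section plans a claim of maintained benefit from CGI-S. This stands, and it is why the point is a low-severity improvement and not a departure from protocol.

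**CGI-I already rates change.** If no subject changed, CGI-I should show few responders and so contradict a falling CGI-S mean. This stands in part. But CGI-I is observed-case too, neither SAP 5.11.4 nor protocol 7.3 states the time point against which improvement is judged, and CGI-I does not show how ill the remaining subjects were at baseline.

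**Attrition is visible.** Each table gives n, SAP 5.5 tabulates numbers remaining and reasons by period, and SAP 5.7.1 gives Kaplan-Meier time on treatment. These show that subjects left and why. They do not show the baseline CGI-S of those present at each visit.

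**Paired change has its own limits.** As Case 2 shows, it is not free of selection. The baseline also follows placebo or pimavanserin 10, 20 or 40 mg in the core study, so a pooled change mixes new starters with subjects already treated. Both limits stand. The fix therefore adds a split by prior treatment and a stated caveat.

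**A stronger reading.** A reader might infer that the table is biased towards apparent benefit, or that a falling mean would come from sicker subjects leaving. The documents do not support that. They give no retention and no link between CGI-S and leaving, and they list psychosis improvement as a withdrawal category alongside progression.

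**Conclusion.** The point holds as a gap in a descriptive summary. A CGI-S baseline is defined, but no planned table uses it for within-subject change, and observed-case means over a shrinking group mix change with selection. With no subject changing, the assumed inputs give a shift of about 0.1 to 0.7 points on the 7-point scale, up or down. This shows what is possible and does not predict what the study will find. The textual facts are firm. The size and direction rest wholly on the assumed baseline distribution, retention and link between severity and leaving. Severity is low: CGI-S is not part of the study objective, nothing is tested, and CGI-I and disposition give partial cover.

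**What to change.** Add to SAP 5.11.3:

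> Change from baseline in CGI-S (baseline = last core-study value, Section 5.4.3) will be summarized by derived visit for subjects with both values, overall, by geographic area and by prior core-study treatment (placebo, pimavanserin 10, 20 or 40 mg), with the baseline mean of those same subjects shown beside each visit.

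Keep the observed-value table. Add a footnote that paired change removes selection on baseline severity but not dropout linked to the change itself.

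The cost is one sentence, a footnote and a few more table columns. No new data are needed: SAP 5.4.3 already relies on the core-study CGI-S, and SAP 5.11.1 already splits SAPS by prior treatment. Some cells by prior treatment may be small at late visits, so n should be shown in each.

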### **5.11.4 Clinical Global Impression – Improvement**

CGI-Improvement (CGI-I) is a single-item score from a 7-point rating scale assessed only at post-baseline visits and is used to assess the improvement in subjects' overall psychotic condition. The 7-point scale ranges from 1 (Very much improved) to 7 (Very much worse). Scores of 0 indicate 'Not Assessed' and will be converted to missing.

The observed values for Clinical Global Impression of Improvement (CGI-I) will be summarized by visit. Additionally the proportion of CGI-I responders [with responder defined as a subject with a score of 1 (very much improved) or 2 (much improved)] will be summarized by visit. A CGI-I rating of 1 (very much improved) or 2 (much improved) represents the point at which clinically meaningful improvement in psychotic symptoms would be expected.

The observed mean values and the CGI-I responders data will also be summarized within each geographic area (North America and outside North America).

### **5.11.5 Resource Utilization in Dementia Scale – Lite**

RUD-Lite, a health economics measure, will be collected at baseline, Month 12 and every 6 months thereafter. The individual item scores will be presented in a data listing. Additional analyses may be conducted and reported separately.

## **5.12 Interim Analyses and Data Safety Monitoring Board**

To provide an adequate update of the long-term safety profile for pimavanserin's new drug application (NDA) submission, a data snapshot was taken on 13DEC2013 and an interim analysis will be performed.

There is no Data Safety Monitoring Board (DSMB) for this study. Safety data are monitored throughout the study and aggregate safety reports are produced and reviewed approximately quarterly.

## 5.13 Analysis of Safety Data

All safety data summaries will be based on the safety analysis set.

### 5.13.1 Adverse Events

AEs started between first study dose date and 30 days after the last dose date will be considered treatment-emergent AE (TEAEs). Any AEs with a completely missing start date will be considered as TEAEs. All AEs and TEAEs will be summarized. In addition, the number of TEAEs, and the number and percent of unique subjects with TEAEs will be summarized by system organ class (SOC) and preferred terms. For SAEs, the SAE onset date will be used in place of the AE onset date for the determination of treatment-emergent status and for assignment of the event to time windows and onset age groups.

AEs will be summarized in terms of the proportion of subjects as well as number of events. When calculating the proportion of subjects with AEs by time period or age group each subject will be counted in the numerator at most once and any repetitions will be ignored; the denominator will consist of all safety-evaluable subjects in the specified time period or age group. When calculating the number of events, each unique record in the database will be counted once.

Additional summaries of TEAEs will also be tabulated with respect to severity (mild, moderate, severe) and AEs of special interest. Tabulations will also be provided for AEs by maximum severity where a subject with more than one event coded to the same preferred term will be classified according to the most severe event. Similarly, in the tabulation by strongest relationship, a subject will be classified according to the event with the strongest relationship to study drug.

An overall summary of all AEs and TEAEs will be presented. The number and percent of unique subjects with TEAEs will be summarized by system organ class (SOC) and preferred term. The number and percent of unique subjects with TEAEs that are determined by investigators as related (possibly, probably, or definitely) to study drug will also be summarized by SOC and preferred term. Additional summaries of TEAEs will also be tabulated with respect to severity (mild, moderate, or severe), where a subject with more than one event coded to the same preferred term will be classified according to the more severe event. A summary of TEAEs in descending order of frequency by preferred term will also be tabulated. Listings of deaths, serious AEs and AEs leading to study treatment discontinuation will also be provided.

The tabulation of TEAEs will be grouped by (1) time period at AE onset and (2) age at AE onset.

- (1) AEs grouped by time period at AE onset: For all TEAEs, serious TEAEs, TEAEs leading to discontinuation of study drug, and TEAEs of special interest (those that may be expected on the basis of pimavanserin's pharmacology, those of special regulatory interest [suicidality, abuse liability etc], and those commonly associated with current antipsychotics), the count and percentage of subjects will be summarized by time period defined in [Section 5.4.2 Table 2](#). The denominator for a time period will be the number of subjects on treatment

(including a 30-day follow-up) during that particular time period. TEAEs with fatal outcome will be summarized by time period at death.

- (2) AEs by age group at AE onset: For all TEAEs, serious TEAEs, TEAEs leading to discontinuation of treatment, and TEAEs of special interest, the count and percentage of subjects will be summarized by age category at the time of AE onset. Age at onset will be categorized as follows:  $\leq 50$  years, 51 - 60 years, 61 – 70 years, 71 – 80 years and 81 - 90 years. The denominator for an age group will be the number of subjects on treatment (including a 30-day follow-up) while in that particular age group. TEAEs with fatal outcome will be summarized by age group at death.

An AE listing by subject will display all events and will include the verbatim term in addition to the MedDRA SOC and preferred term. This listing will also include all relevant CRF data associated with the event: date of onset, date of last dose, severity, outcome, relationship to study drug, action taken, and seriousness.

In addition, AE tables also will be summarized by age group and onset time period for subject with concomitant antipsychotic use and without antipsychotic use.

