6.2.7. Adverse Events

Adverse events will be recorded for all subjects during the Week 2 visit, Month 1 visit, Month 3 visit, Month 6 visit, Month 9 visit, Month 12 visit and every 6 month visit thereafter, and if a subject withdraws or is terminated from the study, at an End-of-Study visit.

Occurrence of AEs after the informed consent is signed and prior to the first administration of investigational drug in this study will be recorded as part of the Updated Medical History taken on Day 1 (Baseline). Once the first dose of investigational drug is taken on Day 1 any subsequent AEs are to be recorded on the CRF page for AEs.

All AEs must be followed until resolution, until the condition stabilizes, until the event is otherwise explained or is judged by the investigator to be no longer clinically significant, or until the subject is lost to follow-up. The investigator is responsible for ensuring that follow-up includes any supplemental investigations necessary to elucidate as completely as practical the nature and/or causality of the AE. This may include additionally laboratory tests or investigations histopathological examinations or consultation with other health care professionals.

Investigators are not obliged to actively seek AE information from former study participants. However, if the investigator learns of an SAE at any time after a subject has been discharged from the study and the event may reasonably be considered related to the use of the study drug, the investigator should promptly telephone the Medical Monitor.

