Serious Adverse Event	
A serious adverse event (SAE) is any AE with any of the following outcomes:
 

• Results in death;

• Is life-threatening (i.e., the subject was at risk of death at the time of the event; it does not refer to an event which hypothetically might have caused death if it were more severe);

• Requires inpatient hospitalization or prolongation of existing hospitalization;

• Results in persistent or significant disability/incapacity;

• Is a congenital anomaly or birth defect;

• Is an important medical event that may not be immediately life-threatening or result in death or hospitalization but based on appropriate medical judgment may jeopardize the subject or may require medical or surgical intervention to prevent one of the outcomes listed above. Examples of such events are intensive treatment in an emergency room or at home for allergic bronchospasm; blood dyscrasias or convulsions that do not result in hospitalization; or development of drug dependency or drug abuse.

Scheduled Visit	
A scheduled visit is any planned visit per the protocol schedule of events.

Study Day 1	
Study day 1 is defined as the date of first administration of study drug (pimavanserin) in the ACP-103-015 study.

Study Day n	
Study day n represents a visit or assessment that occurs n days relative to the start of study drug in the ACP-103-015 study, computed as: (date of visit – study day 1) + 1 if the date of visit occurs on or after date of first dose; otherwise computed as: (date of visit – study day 1). Note that there is no day 0.

Study Duration	
The duration of the open-label use of pimavanserin will be determined based on clinical evaluations but may continue for as long as this drug is considered to be well tolerated and efficacious, and until such time as pimavanserin is approved and commercially available

Treatment- Emergent Adverse Event      A treatment-emergent adverse event (TEAE) is defined as an adverse event started between first study dose date and 30 days after the last dose date in the ACP-103-015 study.

Treatment Group      All subjects will receive 40 mg of pimavanserin once per day (QD).

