### **5.13.2 Deaths and Other Serious and Significant Adverse Events**

Treatment-emergent SAEs, TEAEs leading to discontinuation from the study or study drug, and TEAEs with fatal outcome will be summarized by time period as given in [Table 2](#) in frequency tables by SOC and preferred term. In addition, the overall AE summary table will also be presented for all events (i.e. treatment-emergent plus non-treatment-emergent events).

Subject listings of SAEs, deaths, and AEs leading to discontinuation of study drug will be provided. These listings will provide all relevant eCRF data for each event including the date/study day of onset, date/study day resolved, date of last dose/study day of last dose, severity, outcome, relationship to study drug, action taken, and seriousness.

Kaplan-Meier estimates of percent surviving subjects at 6 months, 1 year, 1.5 years, 2 years, 2.5 years, 3 years, 3.5 years and 4 years, as well as median survival time will be computed for all subjects and by subgroups: baseline age group ( $\leq 75$  years old or  $>75$  years old), gender (female or male), and geographic area (North America or outside North America). If a subject is deceased, the survival time will be calculated as death date minus first dose date + 1; otherwise the survival time will be censored at the last dose date (for subjects who have discontinued from the study) or database snapshot date (for ongoing subjects).

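### SAP 5.13.1 decides treatment-emergence of a serious AE by its SAE onset date alone, so an on-drug AE that first turns serious more than 30 days after last dose is not a TEAE

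*SAP*

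**What the plan says.** The SAP Definitions describe a TEAE by when the event began: it is "defined as an adverse event started between first study dose date and 30 days after the last dose date" in this study. SAP 5.13.1 opens with the same window, then adds an exception: "For SAEs, the SAE onset date will be used in place of the AE onset date for the determination of treatment-emergent status". The same sentence extends the SAE date to the choice of time window and onset age group. Neither document says what SAE onset date means.

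SAP 5.13.2 limits the main tables of serious outcomes to treatment-emergent events: "Treatment-emergent SAEs, TEAEs leading to discontinuation from the study or study drug, and TEAEs with fatal outcome will be summarized by time period", by system organ class and preferred term. For deaths, SAP 5.13.1 adds: "TEAEs with fatal outcome will be summarized by time period at death". That sets the period of a fatal TEAE. Nothing says that the date of death decides whether the event is treatment-emergent.

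Events that turn serious late can reach the database. Protocol 6.2.7 requires: "All AEs must be followed until resolution, until the condition stabilizes", or until another listed end point. Protocol 4.2 repeats follow-up to resolution or stabilization for subjects withdrawn because of an AE.

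**The concern.** The sentence replaces one date with another; it does not add a second test. For a serious event whose two dates fall on either side of last dose plus 30 days, the Definitions and SAP 5.13.1 give opposite answers. The result under 5.13.1 is perverse: an on-drug event counts as a TEAE while it stays non-serious and stops counting once it worsens late enough. An AE that made the subject stop drug can leave the table of TEAEs leading to discontinuation because of something that happened weeks afterwards.

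Long-term safety and tolerability is the only objective. There is no data safety monitoring board, and the interim analysis supports the marketing application (SAP 5.12). Counts of serious and fatal TEAEs by term and period are central outputs, and because such events are few, each misclassified one shows.

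**Working it through.** There is no planned figure to reproduce: SAP 2.4 gives no sample size and SAP 5.1 plans no formal tests. The check applies the date rules to test cases.

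**Notation.** A = AE onset day, S = SAE onset day, L = last-dose day, all as study days with first dose on Day 1.

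**Rules.**
- Definitions: TEAE if 1 ≤ A ≤ L + 30.
- SAP 5.13.1: for a serious event, TEAE if 1 ≤ S ≤ L + 30; for a non-serious event, A is used.
- Either-date rule (the fix): TEAE if A or S lies in the window.

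**Assumptions for illustration.** S is the day a seriousness criterion was first met, each event is one record, and L = 400, so the window closes on Day 400 + 30 = 430.

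| Case | A | S | Death | Definitions | SAP 5.13.1 | Either date |
|---|---|---|---|---|---|---|
| 1 | 380 | 420 | – | yes | yes | yes |
| 2 | 380 | 430 | – | yes | yes | yes |
| 3 | 380 | 431 | – | yes | **no** | yes |
| 4 | 380 | 445 | 445 | yes | **no** | yes |
| 5 | 380 | 390 | 445 | yes | yes | yes |
| 6 | 380 | 425 | 460 | yes | yes | yes |
| 7 | −5 | 10 | – | no | **yes** | yes |
| 8 | 380 | never | – | yes | yes | yes |

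Cases 3 and 4 are lost under 5.13.1 because the event first became serious after Day 430. Cases 5 and 6 are kept although death came on L + 45 and L + 60. Case 7 is gained.

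**One event followed through the outputs.** Suppose pneumonia starts on Day 200, drug is stopped for it on Day 205, it first becomes serious on Day 238, and death follows on Day 240. The window closes on Day 205 + 30 = 235.
- Definitions: 200 ≤ 235, so it is a TEAE, and belongs in the all, discontinuation, serious and fatal TEAE tables.
- SAP 5.13.1: 238 > 235, so it is in none of the four.
- Still counted: in the Kaplan-Meier analysis of AE-related stopping (SAP 5.7.1) at 205 − 1 + 1 = 205 days, and in survival (SAP 5.13.2) at 240 − 1 + 1 = 240 days. Neither analysis states a treatment-emergent restriction. The subject also appears in disposition by reason and period (SAP 5.5), and the event in the listings and the all-events overall summary.

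**Which date should assign the period.** SAP Table 2 has no AE-onset period before Day 1, so Case 7 cannot be placed by AE onset; by SAE onset (Day 10) it falls in the first 4 weeks. Using different dates in different tables would also split one event. With A = 80 and S = 100, it would be in 1–3 months (Days 29–91) in one table and in >3–6 months (Days 92–183) in another. One date per event in all onset-based tables avoids both problems.

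**The case against.** Four points can be made for the plan.

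- **Split records.** Protocol 6.2.7.1 lets an AE record stop when severity changes and a new one start at sustained worsening. If late worsening is recorded that way, the on-drug record stays a TEAE, and the late record would be non-emergent even by plain AE onset. A reader might infer that the event leaves every TEAE table; that holds only for single-record events. But seriousness is a separate attribute in that section, so an event can turn serious with no change in severity. The substitution also matters only when one event carries two different dates. The documents do not settle how such conversions are recorded.
- **Little late collection.** Protocol 6.2.7 does not oblige investigators to seek AEs actively from former participants, which limits the number of cases. It does not bring it to zero: ongoing AEs are followed, and investigators are to report later SAEs that may reasonably be related to drug.
- **Other outputs keep the event.** This stands, and a reader should not infer that these events vanish from the report or survive only in listings. None of those outputs, however, gives treatment-emergent counts by preferred term and period.
- **The rule has a purpose.** It brings in pre-dose conditions that turn serious on drug, which the Definitions miss. That is a real benefit, and any change should keep it.

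**Conclusion.** The point holds in a narrow form. SAP 5.13.1 conflicts with the Definitions and, read literally, gives the wrong class to an AE that begins on drug and first becomes serious more than 30 days after last dose. For a single-record event the loss is from the system organ class, preferred-term and by-period TEAE tables.

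Two stronger readings are not supported. A reader might infer that a late death removes an event; it does not if the event was already serious within the window, and such an event is tabulated at death. A reader might also infer that the rule always favours the drug. Only the loss side does so; the rule gains events as well, and the net direction is unknown.

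The size cannot be derived from the documents and may be small. The conclusion assumes that SAE onset date means the day seriousness was first met and that late conversions are recorded on the original AE. It is worth correcting because the affected tables bear directly on the only objective and the change is simple.

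**What to change.** In SAP 5.13.1, replace the substitution sentence with text to this effect:

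- SAE onset date is the date on which a seriousness criterion was first met.
- A serious AE is treatment-emergent if its AE onset date or its SAE onset date falls within the period from first dose to last dose plus 30 days.
- In all tables, time period and age group are assigned by the SAE onset date when it lies in that window, otherwise by the AE onset date. A footnote gives the number of events included on AE onset date alone.
- Fatal TEAEs continue to be tabulated at death.

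Amend the TEAE entry in the SAP Definitions to match.

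The cost is one extra derivation; the current sentence already presupposes both dates. Serious and fatal TEAE counts may rise slightly. In the test cases above, the change recovers both lost events and keeps the one the present rule gains.
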